# **PROTOCOL SYNOPSIS**

TITLE	A Phase 2 Open-label, Single-arm Trial of the Efficacy and Safety of Topical Remetinostat Gel as Neoadjuvant Therapy in Patients with Squamous Cell Carcinoma Undergoing Surgical Resection				
STUDY PHASE	Phase 2				
INDICATION	Treatment of squamous cell carcinoma (SCC) and squamous cell carcinoma in situ (SCC-IS)				
INVESTIGATIONAL PRODUCT	Topical remetinostat gel 1%				
PRIMARY OBJECTIVE	To determine if topical remetinostat gel treatment 3-times-daily (TID) for 8 weeks will decrease SCC tumor area (in mm²) by at least 30%				
	To determine the overall response rate (ORR) of SCC tumors to 8 weeks of TID treatment with topical remetinostat gel				
SECONDARY OBJECTIVE	To assess the safety and tolerability of remetinostat gel 1% when applied topically TID under occlusion for 8 weeks as follows:				
	
 
Incidence, type, and severity of adverse events (AEs)
 
Incidence and nature of serious adverse events (SAEs)
 
				
	Incidence of AEs leading to remetinostat discontinuation or interruption				
	
 
Adherence to the treatment, measured by number of patients discontinuing the treatment (for any reason) and treatment interruptions
 
				
TREATMENT SUMMARY	Apply topical remetinostat gel 1% 3 times daily (TID) under bandage occlusion for 8 weeks				
STUDY POPULATION	Adults of either gender with squamous cell carcinoma (SCC) lesions ≥ 5 mm. See Section 3.1 for detailed eligibility.				
SAMPLE SIZE	30 SCC per-protocol evaluable tumors. The maximum number of subjects contributing evaluable tumors will be 40, but can be less to obtain the 30 SCC per-protocol evaluable tumors. Participating subjects that do not contribute evaluable tumors will not be counted towards this total. It is anticipated that no more than 40 subjects will participate overall.				

# STATISTICAL CONSIDERATIONS

Overall response rate of SCC tumors (Primary Objective and Primary Outcome) in subjects will be defined as at least a 30% decrease in the area of each SCC lesion(s). With a planned analysis on 30 per-protocol evaluable SCCs, this study would provide 91% power to reject an ORR of 15% if the true ORR is 40% or better, at one-sided alpha level of 0.05 with at least 9 responders.

For the Secondary Objective 1, toxicities will be graded according to the National Cancer Institute CTCAE v5.0.

#### **SCHEMA**

Subjects with SCC(s) ≥5mm, willing and able to delay surgical excision by 10-14 weeks

Baseline safety assessment

Tumor photographs and measurements of evaluable lesions and, with consent, research biopsy

Apply topical Remetinostat gel 1% TID under bandaid for 4 weeks.

Clinical tumor response assessment, photographs, and measurements of evaluable lesions

Apply topical Remetinostat gel 1% TID under bandaid for an additional 4 weeks (for a total of 8 weeks)

Week 10-14 Visit: clinical tumor response assessment, safety monitoring, and with consent, research biopsy

Follow up: Weeks 12-18: follow up evaluation for safety monitoring

# LIST OF ABBREVIATIONS AND DEFINITION OF TERMS

ADL	Activities of daily living			
AE	Adverse event			
BID	Twice daily			
CBC	Complete blood count			
CI	Confidence interval			
CR	Complete response			
CTCAE	Common Terminology Criteria for Adverse Events			
CTCL	Cutaneous T-cell lymphoma			
DLT	Dose-limiting toxicity			
DSMC	Data Safety Monitoring Committee			
EKG	Electrocardiogram			
GI	Gastrointestinal			
Hgb	Hemoglobin			
HDAC	Histone deacetylase			
НН	Hedgehog			
IRB	Institutional Review Board			
IV	Intravenous			
LLN	Lower limit of normal			
OS	Overall survival			
PLT	Platelet			
PD	Progressive disease			
PR	Partial response			
PTCH1	Protein patched homolog 1			
QD	Once daily			
RECIST	Response evaluation criteria in solid tumors			
RR	Response rate			
SAE	Serious adverse event			
SCC	Squamous cell cancer / carcinoma			
SCC-IS	Squamous cell cancer/carcinoma in situ			
SD	Stable disease			
Shh pathway	Sonic hedgehog pathway			
SMO	 			
	Smoothened			
TID	Smoothened Three times daily			

#### 1. OBJECTIVES

# 1.1. Primary Objective

Overall response rate of SCC in subjects defined by at least a 30% decrease in SCC tumor area (in mm²) at end of study measurement as compared with baseline measurements. The threshold for positive response will be at least 30% decrease in tumor area (Note: RECIST v1.1 criteria have limited utility for SCCs under 10 mm, and will not be used for that reason).

# 1.2. Secondary Objectives

- Safety assessment of remetinostat after 8 weeks of topical treatment will be evaluated as follows:
  - Incidence, type, and severity of adverse events (AEs)
  - Incidence and nature of serious adverse events (SAEs)
  - Incidence of AEs leading to treatment discontinuation or interruption
  - Adherence to the treatment, measured by number of patients discontinuing the treatment (for any reason) and treatment interruptions

# 2. BACKGROUND

# 2.1 Study Disease

Cutaneous squamous cell carcinoma (SCC) is one of the most common human cancers and is the second most common skin cancer, comprising at least 20% of all non-melanoma skin cancers, affecting approximately 700,000 Americans each year (as non-melanoma skin cancers are not reported to cancer registries, the exact incidence of SCC is not known). Similar to other skin cancers, risk factors for development of SCC include age, lighter skin tones, and importantly, chronic exposure to ultraviolet light. Exposure to ionizing radiation, arsenic, chronic inflammatory processes (such as in chronic wounds), and HPV infection also predispose patients to developing cutaneous SCC. SCC is also more common in patients who have been exposed to arsenic, or have taken photo-sensitizing drugs such as thiazide diuretics. Up to 50% of transplant patients on immunosuppressive therapy develop cutaneous SCC after long-term therapy; these SCCs also tend to behave more aggressively.

Given their frequencies, treatment of non-melanoma skin cancers (NMSC) represents a significant annual cost to the United States health care system. Amongst all cancers treated in the Medicare population, NMSC represented the 5th-most-costly cancer to Medicare overall and represented 4.5% of all Medicare cancer costs. This high expenditure is largely influenced by the high frequency of NMSC rather than a high per-patient cost. The incidence of NMSC has increased since the mid-1960s at a rate of approximately 2% to 8% per year, so overall healthcare spending to treat SCC, with its continually-increasing incidence, is very likely to continue to rise.

While the exact mechanism of pathogenesis in SCC is unknown, multiple genetic mutations have been associated with and are thought to contribute to the development of SCC. Mutations in *p53*, *CDK2NA*, *RAS*, *MYC*, and *KNSTRN*, *NOTCH1*, and *NOTCH2* have all been associated with SCC and MC1R polymorphisms can influence individuals' risk for developing SCC. *EGFR* and *IKK* expression have been found to be predictive of metastatic capability in SCC. A study of conjunctival epithelial tumors suggested that Sonic hedgehog signaling (Shh) pathway

alterations could lead to transformation of intraepithelial neoplasia into invasive squamous cell carcinoma.

# 2.2 Study Agent

Histone deacetylase (HDAC) inhibitors are anticancer agents. Two HDAC inhibitors, vorinostat and romidepsin, were approved by the US FDA for the treatment of cutaneous T-cell lymphoma (CTCL). HDAC inhibitors antagonize tumors by altering the expression of oncogenes or tumor suppressors by modulating the level of acetylation/deacetylation of histones and/or non-histone proteins such as transcription factors. Preclinical studies suggest that HDAC inhibitors may potentially be effective anti-SCC agents, as murine studies have shown HDAC inhibitors can inhibit the growth of SCC cells and SCC tumors both *in vitro* and *in vivo*.

Remetinostat is also known as suberohydroxamic acid phenyl ester (SHAPE); SHAPE Gel; SHP 141; and 4 [[8 (hydroxyamino) 1,8 dioxooctyl]oxy] benzoic acid methyl ester. Remetinostat is a histone deacetylase inhibitor (HDACi) that was designed with a metabolically labile ester bond so that topical application would produce effective local histone deacetylase (HDAC) inhibition in cutaneous lesions while resulting in only negligible systemic HDAC inhibition.

Preclinical studies have demonstrated a role for histone deacetylase 1 and 2 (HDAC1/2) in modulating Gli1 transcription and basal cell carcinoma (BCC) growth in cell lines and mouse models. We conducted an open-label clinical trial of the pan-HDAC inhibitor, remetinostat, as a neoadjuvant treatment for basal cell carcinoma (BCC). Participants applied topical remetinostat 1% gel three times per day under bandage occlusion to BCC(s) for six weeks prior to undergoing surgical excision. The primary outcome was overall response rate (ORR) as measured by at least a thirty percent decrease in BCC greatest diameter. In addition, tumor area was assessed as well as percent of tumors with complete response. Secondary objectives include suppression of Gli1 expression in post-treatment tumors and remetinostat tolerability. This trial has enrolled 17 BCCs tumors, ranging in baseline size from 6-25 mm greatest diameter, with enrollment goal of 30 tumors. Among the 14 BCCs that have completed the trial, the ORR is 64%. The longest tumor diameter of BCCs shrank by an average of 62%, and tumor area was reduced by an average of 70%. 43% (6) of tumors reached clinical resolution. Side effects associated with treatment included grade 1-2 eczematous reaction in 71% (10), and application site pain in 36% (5). Remetinostat gel for BCC offer a potentially effective, nonsurgical intervention for treatment of localized BCCs.

# HDAC inhibitors can suppress growth of SCC tumor xenografts

In one study, vorinostat was found to suppress the proliferation of epidermoid carcinoma cells *in vitro*. Highly-immunosuppressed female athymic mice were injected with epidermoid carcinoma A431 cells; once tumors were palpable, vorinostat or placebo vehicle was injected intraperitoneally. After three weeks, the mice were sacrificed and their tumors analyzed. Treated tumors demonstrated increased acetylation of histone H3 and p53 and apoptosis of tumor cells. Consistent with this finding, histologic evaluation of treated tumors demonstrated large necrotic areas. Further evaluation demonstrated that vorinostat inhibits cell cycle regulatory proteins (with notable reduction in the production of cyclins A (p = 0.002) and E (p = 0.015). Expression of total and phosphorylated ERK, activation of which is known to regulate cell proliferation, was also assessed. Treatment with vorinostat resulted in significant reduction of ERK1/2 phosphorylation. Additional anti-tumor effect is thought to be due to

reduction in phosphorylation of Akt, resulting in reduction of mTOR and its downstream targets (S6 ribosomal protein, p70S6 kinase, and 4E-BP1).

# HDAC inhibitors are well-tolerated and have resulted in promising clinical responses in patients with advanced stage head and neck squamous cell carcinoma

A phase 1 study of 26 patients with advanced stage head and neck SCCs of mixed etiology demonstrated similar to more-favorable safety and tolerability profiles when compared to pre-existing chemoradiation regimens that did not include a HCAC inhibitor. While clinical response to therapy was not the primary endpoint of this phase 1 study, encouraging tumor responses were observed despite the subjects' advanced-stage tumors.

Altogether, the preliminary data suggests HDAC inhibitors are a promising new candidate therapy for SCC.

Remetinostat is a novel histone deacetylase inhibitor (HDACi) that was designed with a metabolically-labile ester bond so that topical application would produce effective local histone deacetylase (HDAC) inhibition in cutaneous lesions while resulting in only negligible systemic HDAC inhibition. Remetinostat is rapidly degraded into primary metabolites SHP-100 and methylparaben. Three studies (an *in vitro* Franz Diffusion Cell assay; a 28-day study in minipigs; and a 90-day study in minipigs) showed that uptake of remetinostat through skin into the systemic circulation was minimal. In both dermal and intravenous (IV) studies in animals, remetinostat was metabolized in the blood rapidly to the primary metabolites. These findings suggest that dermal application of remetinostat largely obviates systemic exposure to the HDAC inhibitor remetinostat and, consequently, sequelae from systemic inhibition of HDAC. This observation was supported by the fact that in a Phase 1 study in patients with cutaneous T-cell lymphoma (CTCL), plasma concentrations of remetinostat were minimal and at or below the lower limit of quantitation of the assay indicating minimal systemic exposure. The lack of measurable levels of remetinostat in blood is consistent with the rapid conversion of remetinostat to its metabolites.

Remetinostat has been tested in a battery of safety pharmacology studies. Remetinostat did not affect the functional observational battery (FOB) parameters in rats given IV doses of up 100 mg/kg/day, which is equivalent to a dose of approximately 970 mg in a 60-kg human subject. Remetinostat also did not inhibit human ether à-go-go-related gene (hERG) current *in vitro* at concentrations up to approximately 32,000 ng/mL and did not affect cardiovascular function in minipigs given IV doses of up to 100 mg/kg, which is equivalent to a dose of approximately 5,700 mg in a 60-kg human subject. Based on the lack of effect observed in these studies, it was anticipated that remetinostat would be unlikely to adversely affect nervous system or cardiovascular system function when administered topically to humans. This observation has been supported by the clinical data, to date.

A program of Good Laboratory Practice (GLP) - compliant toxicity studies evaluated the safety of multiple doses of remetinostat administered IV to rats and administered topically to minipigs. In addition, the genotoxicity of remetinostat and the local tolerance and sensitizing potential of remetinostat and placebo gel solutions were assessed. Remetinostat and placebo gel were tolerated, with only excipient-related local irritation when applied topically, and renal histopathologic changes not relevant in humans when administered IV. The 28-day No-Observed-Adverse-Effect-Level (NOAEL) for remetinostat administered IV to rats was

30 mg/kg/day. When remetinostat gel 1.5% was applied topically in minipigs, the 28-day and 90-day NOAEL of 150 μg/cm² of skin yielded a total dose of approximately 6 mg/kg.

Based on these findings, a phase 1 (SHP-141-001) study was conducted (NCT01433731) in 18 patients with stage IA-IIA MF-CTCL. This randomized, double-blind, placebo-controlled dose-escalating study was designed to evaluate the safety, pharmacokinetics and pharmacodynamics of remetinostat gel administered topically twice-daily up to 28 days in patients. Escalating doses of remetinostat gel, 0.1%, 0.5% and 1%, were administered BID for a maximum of 28 days to 3 cohorts of patients (n = 6 patients per cohort, active:placebo ratio 5:1).

A phase 2, multicenter, open-label, randomized study (SHP-141-003, NCT02213861) to evaluate the efficacy and safety of remetinostat applied topically in 60 patients with stage IA to IIA MF-CTCL was completed in September 2016. Three doses of remetinostat were evaluated in three treatment arms (n = 20 per treatment arm, 1:1:1 randomization). The three dosing regimens of remetinostat (1% QD, 0.5% BID and 1% BID) were tested in this study for between 6 to 12 months.

All doses and schedules of remetinostat were well tolerated. There were three CTCAE Grade ≥3 remetinostat treatment related AEs, with 2/20 patients discontinuing treatment due to remetinostat related AEs, for the highest dose group of 1% gel BID (2/20 and 6/20 for the 1% gel QD and 0.5% gel BID dose groups respectively). There were no remetinostat treatment related systemic adverse events reported in either clinical study, which is consistent with the minimal systemic exposure and very short half-life of remetinostat in human blood.

A phase 1 study in patients with psoriasis resulted in limited efficacy but the safety profile was similar to the MF-CTCL studies; no serious adverse events were seen on this study.

Remetinostat is not currently approved by FDA for any use, and an Investigational New Drug application (IND) is required. This protocol is submitted to IND 134521.

#### 2.3 Rationale

The severity of SCC burden differs widely among patients from those who develop early SCCs, have advanced SCC, or suffer from numerous SCC lesions. In the more severely-affected, such as those who have undergone organ transplantation or are otherwise immunosuppressed, or those with extensive chronic sun exposure, their quality of life is severely affected by the need for frequent, repetitive surgical procedures. Procedures can be time-consuming and expensive, and they inevitably produce scarring. Other patients may have fewer tumor lesions, but they occur in cosmetically-disfiguring areas or near functional areas, where surgery is not ideal.

SCCs are usually treated with surgical excision, with resultant scars that can be disfiguring. Several non-surgical treatments are sometimes utilized to treat SCC and SCC-IS. Cryotherapy can be used for low-risk invasive cutaneous SCCs and SCC-IS, but is less effective than surgery and can be complicated by post-procedure hypopigmentation, hypertrophic scaring, or hair loss of the treated area. Photodynamic therapy (PDT) is an option for patients with non-invasive SCC, but is not a suitable option for invasive SCC given high recurrence rates. Similarly, topical fluorouracil and imiquimod are both used to treat SCC-IS, especially amongst patients who refuse surgical treatment. However, both of these uses are off-label and have significant inflammatory reactions that can cause patients to discontinue their use. For patients with SCCs in areas not suitable for surgical resection, for those who are not surgical

candidates, or for tumors with significant perineural or large nerve involvement, radiation therapy can be considered. However, limitations exist with each of these non-surgical modalities. Additionally, patients who develop multiple SCCs and/or tumors in sensitive areas would likely greatly benefit from additional non-surgical treatment options.

Given the limitations of current treatment modalities and the pre-clinical murine and phase 1 studies that demonstrate HDAC inhibitors impact the proliferation and survival of SCC cells, the topical HDAC inhibitor remetinostat is promising potential therapy for cutaneous SCCs.

# 2.4 Study Design

# For clinicaltrials.gov and Stanford Clinical Trials Directory compliance (see Section 10 for additional information)

- The primary purpose of this study is:
  - To determine if 8 weeks of topical remetinostat gel applied TID under occlusion will suppress SCC growth
  - To determine the overall response rate (ORR) of SCCs after 8 weeks of treatment with topical remetinostat gel 1%, as measured by at least 30% decrease in greatest area (in mm²).
- Subjects with at least 1 biopsy-proven cutaneous SCC will be recruited for this study.
- Subjects will apply remetinostat gel 1% to at least 1 SCC.
- Non-invasive cutaneous SCC lesions, including Bowen's disease, are also eligible for this study
- There is 1 treatment option: Topical remetinostat gel 1% applied 3 times daily.
- The study is a single-arm, open-label design
- For purposes of ClinicalTrials.gov, there is no secondary outcome.

#### 2.5 Correlative Studies Background

There are no planned correlative studies.

#### 3. PARTICIPANT SELECTION AND ENROLLMENT PROCEDURES

# 3.1 Participant Eligibility Checklist

Participant Eligibility Checklist must be completed in its entirety for each subject prior to registration. The completed, signed, and dated checklist must be retained in the subject's study file and the study's Regulatory Binder.

The study coordinator, treating physician and an independent reviewer must verify that the participant's eligibility is accurate, complete, and legible in source records. A description of the eligibility verification process should be included in the EPIC or other Electronic Medical Record progress note.

Pr	otocol Title:	A Phase 2 Open-label, Single-arm Trial to Investigate the Efficacy and Safety of Topical Remetinostat Gel as Neoadjuvant Therapy in Patients Undergoing Surgical Resection of Squamous Cell Carcinoma (SCC)						
Pr	otocol Number:	IRB-49542 / OnCore TBD						
Pr	incipal Investigator:	[name], PhD						
II.	Subject Informat	ion:						
Sı	ıbject Name / ID:							
G	ender:	☐ Female						
Ш	. Study Information	on:				_		
		B-approved Contract signed						
		lusion Criteria B-approved protocol)	Yes	No	N/A	Supporting Documentation*		
1	greater than or equal	e cutaneous SCC or SCC in situ lesion to 5 mm. Non-invasive SCC lesion(s), re eligible, but must be amenable to						
2	18 years of age or old	er						
3		ly the topical remetinostat 3 times daily r with an occlusive bandage.						
4	dose of study therapy (WCBP), defined as a undergone a hystered	nancy test within 14 days prior to the first [for women of child-bearing potential sexually mature woman who has not stomy or who has not been naturally t least 24 consecutive months (e.g., who time in that period)]						
5	patients with a female agree to use acceptal pregnancy (e.g., oral; contraceptive; tubal li- contraceptive with spe	en of child bearing potential and male partner of child-bearing potential must ble methods of contraception to avoid injectable; or implantable hormonal gation; intra-uterine device; barrier termicide; or vasectomized male) before herapy and for 3 months after the rapy						

	Inclusion Criteria (From IRB-approved protocol)	Yes	No	N/A	Supporting Documentation*
	Has signed and dated the current IRB-approved informed consent document				
	Exclusion Criteria (From IRB-approved protocol)	Yes	No	N/A	Supporting Documentation*
1	Any large (> 20 mm) SCC lesion. Patients with large SCC lesion(s) will be referred for evaluation for surgical resection.				
2	Inoperable locally-advanced and/or non-cutaneous metastatic SCC				
3	SCC lesion(s) in cosmetically-sensitive areas (e.g., tip of nose, eyelid). If a prospective subject has SCC lesion(s) in other areas, those tumor(s) may be considered for enrollment.				
4	Taking any medication known to affect SCC growth				
5	Within the past 6 months, has used topical or systemic therapies that might interfere with the evaluation of the study medication during the study. Specifically, these include the topical use at the site of the study tumors:  Output  Glucocorticoids  Retinoids either systemically or topically at the tumor site (e.g., etretinate, isotretinoin, tazarotene, tretinoin, adapalene)  Alpha-hydroxy acids (e.g., glycolic acid, lactic acid) to the tumor site  S-fluorouracil or imiquimod:				
6	Has received treatment with systemic chemotherapy within 60 days prior to starting study medication				
7	Currently receiving systemic medications that could affect SCC tumors (e.g., oral retinoids) or might interact with remetinostat				
8	Uncontrolled intercurrent illness including, but not limited to, ongoing or active infection, recurrent seizure history or psychiatric illness/social situations that would limit compliance with study requirements				
9	Moderate to significant immunosuppression (e.g., active cancer, significant autoimmune disease) and/or receiving immunosuppressive drugs that result in moderate to significant immunosuppression (e.g., low dose oral glucocorticoids do not necessarily exclude a patient)				
10	Known or previous hypersensitivity to HDACi				
11	History of congestive heart failure, cardiac arrhythmias, or other findings of ventricular dysfunction				
12	Pregnancy or breast-feeding				

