#### 4. TREATMENT PLAN

Adult subjects in the clinic who have one or more biopsy-proven cutaneous SCC or SCC-in situ (hereafter referred to as "SCC") lesions greater than or equal to 5 mm in diameter, at least one of which is being biopsied as a normal course of care, will be invited to participate in this trial. Eligibility of prospective participants will be confirmed, and subjects will enroll according to stated inclusion and exclusion criteria.

Screening visits may be combined with or without day 1 visit.

Prospective participants must be willing to sign a consent form. Subjects will also give consent to donate their SCC tissue for biomarker measurement and apply medication 3-times daily under bandage occlusion for 8 weeks. The anticipated bandage will be an adhesive bandage (e.g., "Band-Aid") with a non-adherent dressing, or paper tape with a non-adherent dressing.

Drug treatment: Subjects will be instructed to apply topical remetinostat to individual SCCs 3-times daily (TID) for 8 weeks. Patients will be asked to discontinue application of the medication at 8 weeks, approximately 2 weeks prior to their surgical excision(s), as dermal irritation from study drug may interfere with lesion identification at excision.

At least 1 target SCC will be identified requiring surgical excision per standard of care. In addition to being measured and photographed, this lesion(s) may be biopsied. Week 8 biopsy may be collected at the time of surgical excision of lesion(s). Histopathological evaluation of the specimen may be performed.

After an initial treatment application demonstration by the study team, treatment applications will be self-administered by the subject or a caregiver. Patients will receive oral and written administration instructions at the outset of the trial as follows:

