Given the absence of any remetinostat treatment related systemic AEs, together with the lack of effect on laboratory parameters or EKG, the minimal levels of remetinostat detected systemically reported in clinical studies to date, and the small BSA (< 0.5%) that will be treated with remetinostat gel, no lab assessments will be performed with the exception of a serum pregnancy test for women of child-bearing potential at baseline to assess eligibility for enrollment.

It is anticipated that the entire target tumor(s) will be surgically removed after the 8th week of treatment, in accordance with regular medical care; it is estimated that the surgical excision will occur between Weeks 10 to 14, depending on surgeon availability. A dose of remetinostat will be applied to the SCC by study personnel in clinic 30 mins before surgical excision. If surgical excision is delayed, i.e., does not occur at Week 10, remetinostat application may be continued for up to 4 additional weeks until surgical excision.

A follow-up visit will occur between Weeks 12 to 18 (approximately 2 to 4 weeks after Mohs/surgical excision), which may be in conjunction with surgery or a surgical follow-up visit,

or the visit may be conducted by phone. Patients may be contacted after completion of the study for additional follow up if deemed necessary by the Study Doctor.

SCC tissue biopsies will be collected from those who consent at baseline and Week 10 to evaluate the tumors treated with topical remetinostat gel 1%. The SCC biopsy will be collected in RNA later.

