# 9. STUDY CALENDAR

	Pre-treatment Day -2 to -30	Pre-treatment Day -1	Treatment Day 1	Treatment Week 4 (+/- 1 week)	Week 10 Visit* (+ 4 weeks)	Follow-up Week 12-18*	Early termination	
Remetinostat treatment			x	x	x			
Informed consent	Х							
Medical history	Х							
Concurrent meds	X							
Physical exam	Х	Х		Х	Х		Х	
Vital signs	Х	Х		Х	Х		Х	
Height	Х							
Weight	Х	Х		Х	Х		Х	
ECOG score	Х			Х	Х		Х	
Serum pregnancy test	Х							
Adverse event evaluation			X					
Tumor measurements and photographs		х		Х	x		x	
Tumor Biopsy		Х				(X)		
Patient Calls			X					

\*Week 10 visit may occur between weeks 10-14, depending on surgeon availability. Study drug will be applied for 8 weeks in total; if surgical excision is delayed, the study drug may be applied for up to 4 additional weeks (for a total of up to 12 weeks)

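### Inclusion 4 and the study calendar give different windows for the only pregnancy test, so the calendar permits a test that is too old for the criterion

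*Combined protocol and SAP*

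**What the plan says.** Three places in the combined protocol and SAP deal with the test.

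- **Section 3.1, Inclusion 4.** The test must be a "nancy test within 14 days prior to the first" "dose of study therapy (WCBP), defined as a" sexually mature woman who meets the stated conditions. The window is therefore 14 days, and it is counted back from the first dose.
- **Section 9, Study Calendar.** The row "Serum pregnancy test" has a single mark, in the column "Pre-treatment Day -2 to -30". Consent, medical history and height share that column. Day -1, Day 1 and the later visits have no mark in this row. The calendar's one footnote concerns the Week 10 visit.
- **Section 4, Treatment Plan.** No laboratory assessments are planned apart from "a serum pregnancy test for women of child-bearing potential at baseline to assess eligibility for enrollment". The text gives no number of days.

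Two further statements bear on timing. Section 3.1 says that the "Participant Eligibility Checklist must be completed in its entirety for each subject prior to registration". Section 4 says that "Screening visits may be combined with or without day 1 visit", so the interval between screening and first dose can differ from one subject to the next.

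**The concern.** The criterion and the schedule give different limits for the same test, and neither refers to the other. Someone who books visits from the calendar sees up to 30 days. Someone who completes the checklist sees 14. A woman tested on Day -25 and first dosed on Day 1 is on schedule by the calendar but does not meet Inclusion 4. The calendar has no later test that would bring her back within the criterion, and Section 4 read literally leaves no room for one.

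The order of events adds to this. The checklist is completed before registration, but the 14 days run to the first dose. If Day 1 slips after registration, an entry that was correct when made can stop being correct, and no visible text asks for the date to be checked again at dosing.

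What is at stake is participant protection and clean eligibility records. Pregnancy is an exclusion (Exclusion 12), Section 7.1 says that the drug's effect in pregnancy is unstudied, and this is the only laboratory test in the trial.

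**Working it through.** The plan states no figure to reproduce here, so the check compares two windows of days.

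**Inputs**
- Criterion: at most 14 days before the first dose (Section 3.1, Inclusion 4).
- Calendar: Day -30 to Day -2, first dose on Day 1 (Section 9).
- Other scheduled pregnancy tests: none (Section 9). Other laboratory tests: none (Section 4).

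**Length of the calendar window**
30 - 2 + 1 = 29 days.

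**Days outside the criterion, no Day 0.** Day -k is then k days before Day 1, and the test is out of window when k > 14.
- Outside: Day -30 to Day -15, that is 30 - 15 + 1 = 16 days.
- Inside: Day -14 to Day -2, that is 14 - 2 + 1 = 13 days.
- Check: 16 + 13 = 29. Share of calendar days outside: 16/29 = 55%.
- Earliest permitted test: 30 days before the first dose, which is 30 - 14 = 16 days too early.

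**Days outside the criterion, Day 0 counted.** Day -k is then k + 1 days before Day 1, and the test is out of window when k + 1 > 14.
- Outside: Day -30 to Day -14, that is 17 of 29 days.
- Inside: Day -13 to Day -2, that is 12 days.
- Earliest permitted test: 31 days before the first dose, which is 17 days too early.

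The documents do not say whether a Day 0 exists. The result moves by one day either way, and the conclusion does not change.

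**Is the calendar mark read correctly?** The table was extracted from PDF, so this needs checking. The mark follows directly after the row label, as it does for informed consent and medical history. Rows with later marks, such as adverse event evaluation, keep their empty cells before the mark. Reading it as the first column is sound.

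**The case against.** The strongest reply is that this is no true contradiction. Day -2 to Day -30 is the window for the whole screening visit, not a rule for the pregnancy test, and an eligibility criterion may be narrower than the visit in which it is assessed. Section 4 ties the test to eligibility, so a site must honour both texts, and it can: every day from Day -14 to Day -2 satisfies both. Section 3.1 also has three people verify eligibility (coordinator, treating physician and independent reviewer) against an item that contains the 14-day limit. Where screening is combined with Day 1, there is no gap at all.

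Most of this stands, and it limits the point: the calendar permits an out-of-window test and does not require one. It does not remove the mismatch. Verification takes place before registration, while the criterion is anchored to the first dose. The interval between the two is not given, and neither a re-check nor a repeat test appears in the text available. One reservation applies: the supporting-documentation column of the checklist carries an asterisk whose note is not visible, and the page after the checklist is not in the text reviewed.

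A reader might go further in three ways that the documents do not support.
- **That 55% is a risk.** It is a share of calendar days. The documents give neither the distribution of screening-to-dose intervals nor the number of women of child-bearing potential.
- **That pregnant women would be treated.** An old test leaves Inclusion 4 unmet and says nothing about pregnancy. Inclusion 5 separately requires contraception, and Sections 4.2 and 7.2 provide for discontinuation and follow-up if pregnancy occurs.
- **That affected lesions would leave the response-rate denominator.** Sections 12.1 and 12.4.2 do refer to eligible and treated lesions. But Section 12.4.1 defines the analysis population by consent to treatment and at least one SCC tumor, and the per-protocol set by at least 80% compliance. Neither depends on when the test was done.

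**Conclusion.** The plan is wrong as written on this point, as a minor internal inconsistency. Inclusion 4 allows 14 days before the first dose, while the calendar's only test may fall up to 30 days before. With no Day 0, 16 of the 29 permitted days lie outside the criterion; with a Day 0, 17 of 29. The finding rests on the single calendar mark belonging to the screening column, and on there being no re-check or repeat test in pages that were not available.

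The number of women concerned is unknown and may be small: the synopsis anticipates no more than 40 subjects overall, and only women of child-bearing potential are affected. Nothing here touches the primary analysis, the power statement or the sample size. The point is worth correcting because it concerns the trial's one laboratory safeguard for a listed exclusion, and because the correction is cheap.

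**What to change.** Reconcile Section 3.1 (Inclusion 4), Section 4 and Section 9. The criterion and the calendar's pregnancy-test row, the latter through a footnote, should state the same window, counted back from the first dose. The calendar and the Section 4 statement on laboratory tests should also be made consistent with meeting that window when screening and Day 1 are far apart. Which window stands is for the sponsor to decide; this review does not propose one.

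The cost is a calendar footnote with matching wording in the next amendment and, depending on the window kept, an occasional repeat test.
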